6.3.2 Concomitant Therapy

Not Permitted:

- Concomitant use of immunosuppressant medication, other than low-dose corticosteroids, unless rescue criteria ([Appendix 1](#)) are triggered.
- Concomitant use of known strong to moderate inducers or inhibitors of CYP3A ([Appendix 2](#)) within 14 days or 5 half-lives (whichever is longer) of dosing with PRN1008.
- Use of CYP3A-sensitive substrate drugs ([Appendix 3](#)) with a narrow therapeutic index within 14 days or 5 half-lives (whichever is longer) of PRN1008 dosing including, but not limited to, alfentanil, astemizole, cisapride, cyclosporine, dihydroergotamine, ergotamine, fentanyl, pimozone, quinidine, sirolimus, tacrolimus, or terfenadine.
- Proton pump inhibitors are not permitted. Esomeprazole was shown to reduce the exposure of PRN1008 by approximately 50%, presumably due to the effects of a lack of an acidic environment on tablet dissolution. Therefore, subjects who are on proton pump inhibitors should be changed to H2 receptor blocking drugs if possible or not enrolled in the study.

Permitted:

- The use of oral prednis(ol)one may be permitted in some circumstances. For admission to the study, doses of oral prednis(ol)one in the 2 weeks prior to Day 1 may be no higher than 0.5 mg/kg per day (inhaled and mucosal [for symptomatic treatment of oral lesions] corticosteroids are allowed). Where patients enter the study on low-dose corticosteroids, the regimen should be maintained for the initial 2 weeks of PRN1008 therapy. At the Day 15 review, a good clinical response to PRN1008 should allow the tapering of the corticosteroid to commence using the Werth taper ([Appendix 7](#)). At all times, the rescue criteria should be followed, as indicated ([Appendix 1](#)). In some circumstances, corticosteroids should be added or the dose increased, with or without cessation of PRN1008.
- Clinically relevant 3A substrate drugs (e.g., “sensitive substrate” listed in [Appendix 3](#)) should be managed by administering PRN1008 on a time schedule such that CYP 3A substrate drugs can be given 2 hours or more after PRN1008.
- H2 receptor blocking drugs and antacids are permitted provide PRN1008 is given at least 2 hours beforehand.
- Anticoagulation with warfarin should be monitored actively in the first weeks of PRN1008 therapy, as the combination has not been studied previously.

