1.2 Rationale for PRN1008 Treatment in Pemphigus

PV is known to be driven by autoantibodies to epidermal proteins and is responsive acutely to the anti-inflammatory effects of corticosteroids and within 5 to 35 weeks to B- cell depletion by anti-CD20 therapy (Horvath et al. 2012).

PRN1008 is a novel, highly selective, small molecule inhibitor of non-T cell white blood cell signaling (via B- cell receptor, FC γ R, Fc ϵ R signaling of the Bruton's tyrosine kinase, i.e., BTK, pathway).

In Phase 1 studies with 114 healthy volunteers, target BTK occupancy levels were safely and consistently exceeded, suggesting PRN1008 at the planned dose levels may be highly effective in human pemphigus and other autoimmune diseases.

As of January 18, 2018, PRN1008 had been administered to 21 patients with pemphigus (pemphigus vulgaris [PV] and pemphigus foliaceus [PF]), 18 of whom had 4 or more weeks of treatment with PRN1008. Of the 18 patients with efficacy data, 11 (61%) met the primary endpoint of "Control of Disease Activity" (CDA) on a CS dose of ≤ 0.5 mg/kg/day (low-dose CS) by the Week 5 visit. Three patients achieved CDA on no CS. Two patients required high-dose CS temporarily during PRN1008 treatment due to worsening of disease activity. Four patients achieved complete remission (CR) on 1 to 20 mg/day of CS; 3 achieved CR at Week 13 (25%) and one achieved CR at Week 21. PRN1008 has been well-tolerated in this study (see [Section 1.4](#)).

Refer to [PRN1008 Investigators' Brochure](#) for additional information.

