2 RATIONALE AND JUSTIFICATION FOR THE STUDY AND THE STUDY DESIGN

2.1 Rationale for the Study Design

This open-label, pilot study is designed to explore the initial efficacy and safety of PRN1008 in PV and to enable the accurate design of pivotal randomized clinical trials which are to follow. An open-label design was chosen for several reasons: PV does not spontaneously remit so there is no placebo effect to account for; clinicians need to know when to use rescue corticosteroids, if necessary, in a timely manner; and lastly, the pilot nature of the investigation itself is best explored in an open-label fashion.

Because of the ability to guide individualized dosing with BTK occupancy measurement, the use of which has been validated in a naturally occurring canine pemphigus study, this assay was used to supplement the clinical response assessments in making dose-adjustments in **Part A**. More than 95% of patients in **Part A** (20/21) had adequate BTK occupancies (mean 86% pre dose at steady-state). In **Part B**, the clinical efficacy of the 400 mg qd dose is being explored to see if lower BTK occupancies will still equate to clinical efficacy. For this reason, clinical response alone, and not BTK occupancies, is recommended to guide dose adjustment in **Part B**.

Given the efficacy seen in this pemphigus study to date at varied clinical severities, and the updated, supporting, chronic, GLP toxicology ([Section 1.3](#)), there is clinical equipoise to study PRN1008 monotherapy (or with low dose CS) in patients with mild-to-severe (baseline PDAI 8-60), corticosteroid-naïve or relapsing PV, with close observation and appropriate corticosteroid rescue protocols.

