6.2 Exclusion Criteria

1. Previous use of a BTK inhibitor

*Patients enrolled in a previous version of this protocol who are still in their 12-week active treatment period with PRN1008 are eligible to continue treatment, initially with their current dose level, under this amended protocol for an additional 12 weeks, i.e. 24 weeks total, following review and signature of the EC approved patient's consent. Patients who completed **Part A** and did not discontinue the study due to a medical condition that might compromise safety assessments or for a PRN1008 related adverse event may be screened for entry under **Part B**.*

2. Pregnant or lactating women

3. ECG findings of QTc > 450 msec (males) or > 470 msec (females), poorly controlled atrial fibrillation (i.e. symptomatic patients or a ventricular rate above 100 beats/min on ECG), or other clinically significant abnormalities
4. A history of malignancy of any type, other than surgically excised non-melanoma skin cancers or in situ cervical cancer within 5 years before the day of dosing
5. Use of immunologic response modifiers with the following periods prior to Day 1: as concomitant therapy, other immunologic response modifiers not detailed in this exclusion apart from corticosteroids; *1 week*: cyclophosphamide; *4 weeks*: IVIG, Kinaret (anakinra) and Enbrel (etanercept); *12 weeks*: Remicade (infliximab), Humira (adalimumab), Simponi (golimumab), Orenzia (abatacept), Actemra (tocilizumab), Cimzia (certolizumab), Cosentyx (secukinumab), plasmapheresis; *6 months*: Rituxan/MabThera (rituximab), ofatumumab, any other anti-CD20 antibody, other long-acting biologics
6. More than 0.5 mg/kg of prednis(ol)one per day (“low dose corticosteroids”) within the two weeks prior to Day 1
7. Use of proton pump inhibitor drugs such as omeprazole and esomeprazole (it is acceptable to change patient to H2 receptor blocking drugs prior to the first dose of PRN1008)
8. Concomitant use of known strong-to-moderate inducers or inhibitors of CYP3A ([Appendix 2](#)) within 3 days or 5 half-lives (whichever is longer) of study drug dosing
9. Use of CYP3A-sensitive substrate drugs ([Appendix 3](#)) with a narrow therapeutic index within 3 days or 5 half-lives (whichever is longer) of study drug dosing including, but not limited to, alfentanil, astemizole, cisapride, cyclosporine, dihydroergotamine, ergotamine, fentanyl, pimozide, quinidine, sirolimus, tacrolimus, or terfenadine

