When patients enter the study on corticosteroids, the dose should be maintained for the initial 2 weeks of PRN1008 therapy if possible in order to evaluate the additive effects of PRN1008. During this time and subsequently, the rescue criteria should be followed if indicated. In other words, in some circumstances the corticosteroid dose should be increased, with or without cessation of PRN1008. If patients respond well to PRN1008 without increasing the corticosteroid dose, the Werth taper ([Appendix 7](#)) should be commenced after four weeks of PRN1008 therapy.

* As defined by the EADV 2014 Pemphigus S2 Guideline ([Hertl et al. 2015](#))

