Table B.14.2.1.5.3 Proportion of patients Achieved CDA at or Prior to Week 5 without prednis(ol)one >0.5 mg/kg – Subgroup – Pemphigus History (PP Population)

Note: Subgroups are: ‘Newly diagnosed (\leq 6 months from screening)’, ‘Relapsed (>6 months from screening)’

Additional footnote: Newly diagnosed is defined as subjects who were diagnosed at most 6 months prior to date of screening, otherwise the subject is relapsed.

Table B.14.2.1.6.1 Proportion of patients Achieved CDA at or Prior to Week 5 without prednis(ol)one >0.5 mg/kg – Subgroup – Baseline Pemphigus Anti-DSG Profile (mITT Population)

Table B.14.2.1.6.2 Proportion of patients Achieved CDA at or Prior to Week 5 without prednis(ol)one >0.5 mg/kg – Subgroup – Baseline Pemphigus Anti-DSG Profile (Completer Population)

Table B.14.2.1.6.3 Proportion of patients Achieved CDA at or Prior to Week 5 without prednis(ol)one >0.5 mg/kg – Subgroup – Baseline Pemphigus Anti-DSG Profile (PP Population)

Note: Subgroups are: ‘Pemphigus Vulgaris (PV)’, ‘Pemphigus foliaceus (PF)’ and ‘Negative anti-DSG profile’

Table B.14.2.1.7.1 Proportion of patients Achieved CDA at or Prior to Week 5 without prednis(ol)one >0.5 mg/kg – Subgroup Analysis – Baseline Pemphigus Severity (mITT Population)

Table B.14.2.1.7.2 Proportion of patients Achieved CDA at or Prior to Week 5 without prednis(ol)one >0.5 mg/kg – Subgroup Analysis – Baseline Pemphigus Severity (Completer Population)

Table B.14.2.1.7.3 Proportion of patients Achieved CDA at or Prior to Week 5 without prednis(ol)one >0.5 mg/kg – Subgroup Analysis – Baseline Pemphigus Severity (PP Population)

Note: Subgroups are: ‘Mild at Baseline’, ‘Moderate at Baseline’

Additional footnote: Based on PDAI total activity score. For newly diagnosed patients: Mild is 0 to 14 and Moderate is 15 to 44. For relapsed patients: Mild is 0 to 8 and Moderate is 9 to 24.

Table B.14.2.2.1.1 Cumulative Incidence of Patients Achieved CDA by Visit – Cumulative Incidence (mITT Population)

Visit	Achieved CDA	400 mg QD (N = n)	400 mg BID (N = n)	600 mg BID (N = n)	Overall (N = n)
SCREENED	N achieved (%)	x (x.x)	x (x.x)	x (x.x)	x (x.x)
	- 80% CI	x.xx, x.xx	x.xx, x.xx	x.xx, x.xx	x.xx, x.xx
	- 95% CI	x.xx, x.xx	x.xx, x.xx	x.xx, x.xx	x.xx, x.xx
WEEK 1 DAY 1	Cumulative N achieved (%)	x (x.x)	x (x.x)	x (x.x)	x (x.x)
	- 80% CI	x.xx, x.xx	x.xx, x.xx	x.xx, x.xx	x.xx, x.xx
	- 95% CI	x.xx, x.xx	x.xx, x.xx	x.xx, x.xx	x.xx, x.xx
WEEK 1 DAY 2	Cumulative N achieved (%)	x (x.x)	x (x.x)	x (x.x)	x (x.x)

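### Entry caps the steroid dose but does not require it to be stable, so CDA after a recent steroid start or increase counts as a primary response; separately, Part B's secondary cumulative tables begin before the first dose

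*Protocol*

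**What the plan says.** **Before Day 1.** Protocol section 6.3.2 states that "doses of oral prednis(ol)one in the 2 weeks prior to Day 1 may be no higher than 0.5 mg/kg per day". Exclusion criterion 6 (section 6.2) is the mirror image: "More than 0.5 mg/kg of prednis(ol)one per day (“low dose corticosteroids”) within the two weeks prior to Day 1". Both set a ceiling. Neither requires a constant dose or a minimum time on it.

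**After Day 1.** For patients who enter on low-dose steroid, section 6.3.2 says "the regimen should be maintained for the initial 2 weeks of PRN1008 therapy". Appendix 1B gives the purpose: "the dose should be maintained for the initial 2 weeks of PRN1008 therapy if possible in order to evaluate the additive effects of PRN1008"; Appendix 1A has the same instruction for Part A. Otherwise systemic steroid is to be avoided unless a rescue criterion is met.

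**Design rationale.** Section 2.1 defends the uncontrolled design on the ground that "PV does not spontaneously remit so there is no placebo effect to account for". Section 1.2 says of the same disease that it "is responsive acutely to the anti-inflammatory effects of corticosteroids".

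**Responder rules.** Part A SAP section 8.1 makes a patient a non-responder if any daily dose above 0.5 mg/kg occurs before first CDA. Part B SAP section 5.4.1 looks only at the dose on the day before CDA. Both require CDA after the first PRN1008 dose and by the Week 5 visit. Neither compares the dose with an earlier one.

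**Part B cumulative shells.** Tables B.14.2.2.1.1 (CDA) and B.14.2.2.8.1 (CR) open with a Screening row. The next row, Week 1 Day 1, is already labelled "Cumulative N achieved". Part B SAP section 5.4.2.1 gives no post-dose starting point. The corresponding Part A shells (Tables 14.2.2.4.4.1 and 14.2.2.5.4.1) start at Week 3.

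**The concern.** CDA is an early and modest milestone: new lesions have stopped appearing and existing ones have started to heal. It is read within 4 weeks, a period in which a newly started or increased steroid could itself produce it. With no control arm, the response rate supports PRN1008 only if nothing else that acts this quickly changed around Day 1. The absence of spontaneous remission does not settle that, because the competing explanation is a treatment which the protocol itself calls fast-acting.

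Recent starts are foreseeable. Section 6 admits newly diagnosed patients who have not yet had effective induction treatment, inclusion criterion 2 allows entry on low-dose steroid, and screening may last 28 days. Holding the dose for two weeks after Day 1 isolates an additive effect only if the patient was already on a steady dose before Day 1.

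Section 11.4 says the results will be used to design confirmatory trials, so an inflated rate would carry forward. The Part B shells raise a separate, smaller problem: control recorded before any PRN1008 would stay in the numerator at every later visit.

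**Working it through.** **1. The plan's own precision figure.** Protocol section 11.4 assumes a 50% response rate and 25 patients per Part, and states an 80% CI of ±13%.
- Normal approximation: 1.2816 × √(0.5 × 0.5 / 25) = 1.2816 × 0.1 = 12.8 points. The stated figure is reproduced.
- With the exact (Clopper-Pearson) method that the SAP specifies, 12/25 gives 33.8% to 62.5% and 13/25 gives 37.5% to 66.2%, a half-width of about 14.4 points.

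**2. Tracing a patient through the rules.** Take a patient who starts prednisolone at or below the ceiling within the 14 days before Day 1, keeps that dose as instructed, and is recorded in CDA at Day 15.

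| Rule | Result |
|---|---|
| Exclusion 6 and section 6.3.2 | Eligible: ceiling not exceeded |
| CDA after first dose and by Week 5 | Met |
| Part A: no daily dose above 0.5 mg/kg before first CDA | Met |
| Part B: dose not above 0.5 mg/kg the day before CDA | Met |
| Any test for a recent start or increase | None exists |

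The patient is a primary responder in either Part.

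**3. Size per patient.** 1/25 = 4 points. Three such patients move the rate by 12 points and four by 16, so three or four match the whole stated half-width.

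**4. What the interim Part A data show.** Protocol section 1.2 reports 11 of 18 meeting the primary endpoint: 61.1%, exact 80% CI 43.3% to 76.9%. It also says "Three patients achieved CDA on no CS": 3/18 = 16.7%, exact 80% CI 6.3% to 33.4%. The text does not say whether those three are among the 11. If they are, 11 − 3 = 8 patients (8/18 = 44.4%) reached CDA while on some steroid. The gap of 61.1 − 16.7 = 44.4 points is then an upper bound on steroid involvement. It does not estimate steroid-caused response.

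**5. Illustration on assumed inputs (none is in the documents).** Let p be the true PRN1008 response rate, q the share of patients with a recent steroid start or increase, and s the chance that the steroid alone gives control in such a patient who would not otherwise respond. The observed rate is p + (1 − p) × q × s. With q from 10% to 60% and s from 20% to 50%:
- p = 30%: observed 31.4% to 51.0%
- p = 40%: observed 41.2% to 58.0%
- p = 50%: observed 51.0% to 65.0%

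The bias could be trivial or could exceed the planned half-width. The unknown that matters most is q, and q can be counted from the medication records.

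**6. Reach of the pre-dose rows.** In Part B the primary endpoint (section 5.4.1) and the time-to-event analyses (section 5.4.2.2) are limited to events after first dosing. The Screening and Day 1 rows therefore affect only the secondary cumulative CDA and CR tables, including steroid-free CDA, which uses the same shell. The shell is also inconsistent with itself: it assigns patients to the PRN1008 dose taken before CDA, and at Screening there is none.

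**The case against.** **The study is an acknowledged uncontrolled pilot, and several outputs already expose steroid use.** Steroid-free CDA is a secondary endpoint. Table B.14.2.2.23.1 shows the change in steroid dose from Screening to Day 1. Listing B.16.2.6.10 puts steroid dose beside CDA and CR at each visit, and the panel plots overlay steroid dose on each patient's PDAI. This stands in part: a careful reader could see the confounding patient by patient. But no planned table links a pre-entry steroid change to response, and steroid-free CDA cannot separate long-stable users from recent starters.

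**A reader might infer that the Screening rows inflate the primary result.** The documents do not support that, because both primary definitions require CDA after first dose. The shells are also described as adjustable (Part B SAP section 6), and CR at Screening is unlikely given an entry PDAI of at least 8. The rows look like a template fault, and they show only what the layout would permit.

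**A reader might infer that steroid increases after entry are also freely counted.** The protocol limits these. The entry dose is held for two weeks and other systemic steroid needs a rescue trigger. Where rescue criterion 2 adds steroid it goes to 1.0 mg/kg, above the endpoint limit, and rescue criterion 3 applies only after CDA has not been reached by 4 weeks. What remains inside the primary window is mainly deviations.

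**A reader might discount some of the eight steroid-treated responders to obtain a corrected rate.** The documents do not give the share with a recent change, and removing those patients from the numerator alone would assume that PRN1008 did nothing for any of them. Nor is 3/18 a fair steroid-free rate, because patients who entered on steroid were told to stay on it for two weeks.

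**Conclusion.** The concern holds in two separate parts.

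**Primary endpoint, both Parts.** Entry fixes a ceiling without stability, and no responder rule detects a recent start or increase at or below it. In such patients CDA within 4 weeks is credited to PRN1008 although the design cannot attribute it. The number affected is unknown. Each one is worth 4 points at n = 25, so three or four would equal the planned half-width. This rests on the protocol's own statement that the disease responds acutely to steroid. It does not show that the 61% interim rate is wrong or by how much.

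**Secondary cumulative tables, Part B only.** As laid out, they would carry forward control recorded before the first dose. The primary and time-to-event analyses are not affected. One loose end remains in the primary analysis: requiring the first CDA to follow the first dose suggests that a patient already in CDA on Day 1 cannot be a responder, but section 5.4.1 does not say so for a patient in CDA both before and after dosing.

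**What to change.** 1. **Stratify the primary endpoint.** Using medication dates already collected (Protocol section 16.12 goes back 28 days before screening), tabulate it by systemic steroid status before Day 1: none; unchanged for the 14 days before Day 1; started or raised within those 14 days.
2. **Add a sensitivity analysis.** Count any start or increase of systemic steroid from 14 days before Day 1 to first CDA as non-response, and show the result beside steroid-free CDA.
3. **Start the Part B cumulative CDA and CR tables at the first post-dose visit.** State that CDA or CR already recorded at Screening or Day 1 is not a response to PRN1008 in the cumulative or primary analyses.

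The cost is SAP and shell wording and a little more analysis, with no new data. The strata will be small, and the supporting rate may be less favourable. The Part B SAP is marked final on 24 February 2020, so additions should be dated and labelled as supportive.

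The entry steroid rule is a matter for the sponsor, who should reconcile the ceiling-only condition in sections 6.2 and 6.3.2 with the aim in Appendices 1A and 1B of evaluating PRN1008's additive effect.

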7 LIST OF SCREENING ASSESSMENTS

The Schedule of Assessments is presented in [Appendix 4](#). All participants must sign and date the most current Institutional Review Board (IRB)-approved written informed consent form before any study specific assessments or procedures are performed. An original signed consent form will be retained by the Investigator and the participant will be given a copy of the signed consent form.

Participants must fulfill all entry criteria to be enrolled into the study. Participants who fail to meet the entry criteria may be rescreened once at the discretion of the Investigator. A record of eligibility screening documenting the Investigator's assessment of each screened participant with regard to the protocol's inclusion and exclusion criteria, including screen failures, is to be completed and signed by the Investigator or designee. Ethnicity of participants will be recorded, since this information might be important to evaluate a potential impact of ethnic factors on drug properties [see also ICH Guideline E5 (R1)].

Up to 28 days before enrollment in the study, participants will be required to sign a consent form, after which screening assessments will be carried out. After providing written informed consent, subjects will complete the Screening Assessments within 28 days before the first dose of PRN1008:

- Review of medical history and concomitant medication
- PDAI, ABSIS assessments
- Review of inclusion and exclusion criteria
- Measurement of height and weight
- Physical examination
- 12-Lead ECG
- Vital signs (blood pressure, heart rate, respiration rate, and temperature)
- Clinical laboratory testing (hematology, coagulation, serum chemistry, and urinalysis)
- HIV, hepatitis B (surface antigen and core antigen and antibodies), hepatitis C (anti-HCV antibody confirmed with Hep C RNA)
- TB screen with T-spot TB Test, QuantiFERON®-TB Gold, or QuantiFERON®-TB Gold Plus (QFT Plus)
- Serum pregnancy test for females of child bearing potential
- FSH (in postmenopausal women who are not surgically sterile only)
- Skin biopsy if not already performed: lesional for H&E staining, perilesional for direct immunofluorescence

8 LIST OF STUDY ASSESSMENTS

The Schedule of Assessments is presented in [Appendix 4](#).

8.1 Clinical Assessments Part A and B

- Medical history, including evaluation of any on-study AEs and periodic vital signs (body temperature, heart rate, respiratory rate, blood pressure), concomitant medication use, full or abbreviated physical examination
- At screening only: height and weight, full physical examination, and 12-lead electrocardiogram (ECG) (an extra ECG may be taken at additional visits, if indicated)
- Disease activity scores (PDAI, Autoimmune Bullous Skin Disorder Intensity Score [ABSIS]) ([Appendix 5](#))
- Standardized photography of the affected area (Optional)
- Autoimmune Bullous Diseases Quality of Life (ABQOL) and Treatment of Autoimmune Bullous Diseases Quality of Life (TABQOL) assessments ([Appendix 5](#))
- SNAQ appetite questionnaire ([Appendix 6](#))

